## **2 Sample size determination**

---

The aim is to enrol a total of 1500 HCW (750 BCG and 750 placebo). For a detailed sample size calculation, please refer to the protocol.

---

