## 9 Analysis of the exploratory endpoints

---

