### 9.1 Safety endpoints: (Serious) adverse events (AE / SAE) and suspected unexpected serious adverse reactions (SUSAR)

Frequencies of AEs, SAEs and SUSARs will be described per intervention arm for total number of events, per solicited event, and for unsolicited events. Frequencies of having at least one AE / SAE / SUSAR will be compared using logistic regression analysis and reported as OR with 95% CI.

For the following endpoints, the same modelling approach will be used as for endpoint 8.2 Cumulative incidence of COVID-19 disease:

- 9.1.1 the cumulative incidence of hospital admission for any reason
- 9.1.2 the cumulative incidence of intensive care admission for any reason
- 9.1.3 the cumulative incidence of death for any reason

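### SAP section 9.1 gives an odds ratio for any adverse event but none for unsolicited events alone, so an effect on non-serious unsolicited events can be hidden

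*SAP*

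**What the plan says.** Section 9.1 handles adverse events in two steps. The first is descriptive and keeps the two kinds of event apart: "Frequencies of AEs, SAEs and SUSARs will be described per intervention arm for total number of events, per solicited event, and for unsolicited events". The second produces an effect estimate, an OR with a 95% CI: "Frequencies of having at least one AE / SAE / SUSAR will be compared using logistic regression analysis". The second step does not mention the solicited/unsolicited split. Its slashes also do not say whether AE, SAE and SUSAR are three outcomes or one composite.

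The same section then turns to all-cause hospital admission, ICU admission and death: "For the following endpoints, the same modelling approach will be used as for endpoint 8.2 Cumulative incidence of COVID-19 disease". All of this stands under the section 9 heading "Analysis of the exploratory endpoints". Section 10 brings SAEs and SUSARs, but not AEs in general, into the interim reports.

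The SAP does not list the solicited events and gives no expected rate for any kind of adverse event.

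**The concern.** A participant who has had one solicited event already counts as having an AE. A later unsolicited event in that person cannot change the outcome. The more common solicited events are, and the more they differ between arms, the less the any-AE OR says about anything else.

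The trial compares an intracutaneous vaccine with placebo, so a difference in solicited events is possible. The SAP recognises the distinction, but drops it at the one place where AEs in general receive an estimate and an interval. A reader who wants to know whether non-serious unsolicited events were more or less frequent after BCG would have counts by arm and one pooled OR that may point the other way.

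A second, smaller problem is the planned OR for SUSARs. Such events are likely to be very few, and an OR on a handful of events or none carries almost no information.

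**Working it through.** The SAP states no figure for this analysis, so there is nothing to reproduce. What follows illustrates size only. The 750 per arm comes from SAP section 2; **every event rate is an assumption**.

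**Step 1. Formulas.** Let *s* be the risk of at least one solicited event and *u* the risk of at least one unsolicited event. If the two are independent within an arm, the risk of any AE is *p* = 1 − (1 − *s*)(1 − *u*). The pooled OR is [*p*B/(1 − *p*B)] / [*p*P/(1 − *p*P)], with B for BCG and P for placebo. The Wald 95% interval uses SE(log OR) = √[1/(750 *p*B(1 − *p*B)) + 1/(750 *p*P(1 − *p*P))].

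**Step 2. One case in full.** Take solicited 20% vs 5% and unsolicited 15% vs 20%.
- Unsolicited alone: (0.15/0.85)/(0.20/0.80) = 0.71. SE = √(1/95.625 + 1/120) = 0.137, so the 95% interval is 0.54 to 0.92.
- Any AE on BCG: 1 − 0.80 × 0.85 = 0.32. On placebo: 1 − 0.95 × 0.80 = 0.24.
- Pooled OR: (0.32/0.68)/(0.24/0.76) = 1.49. SE = √(1/163.2 + 1/136.8) = 0.116, so the 95% interval is 1.19 to 1.87.

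The two intervals lie on opposite sides of 1.

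**Step 3. A range of assumptions.** Pooled any-AE OR (95% interval), BCG vs placebo:

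| Solicited | Unsolicited 20% vs 20% (OR 1.00) | 30% vs 20% (OR 1.71) | 15% vs 20% (OR 0.71) |
|---|---|---|---|
| 2% vs 2% | 1.00 (0.78–1.28) | 1.66 (1.32–2.10) | 0.73 (0.56–0.94) |
| 5% vs 2% | 1.15 (0.90–1.46) | 1.83 (1.45–2.30) | 0.87 (0.67–1.11) |
| 20% vs 5% | 1.78 (1.42–2.23) | 2.49 (1.99–3.10) | 1.49 (1.19–1.87) |
| 50% vs 10% | 3.86 (3.11–4.79) | 4.78 (3.84–5.94) | 3.48 (2.81–4.31) |

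Where solicited events are rare and equal, the pooled OR follows the unsolicited OR closely. From 20% vs 5% upwards it exceeds 1 in all three columns.

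**Step 4. The independence assumption.** For the case in step 2, suppose the rarer kind of event occurs only in people who also have the other. The any-AE risks are then 0.20 and 0.20, and the OR is 1.00. Suppose instead that nobody has both. The risks are 0.20 + 0.15 = 0.35 and 0.05 + 0.20 = 0.25, and the OR is (0.35/0.65)/(0.25/0.75) = 1.62. With the same extreme in both arms, the reduction is hidden either way, but the reversal of direction depends on how far the events overlap.

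**Step 5. SUSARs.** With the same rate *r* in both arms, the chance of none in one arm is (1 − *r*)^750, and the chance that at least one arm has none is 1 − [1 − (1 − *r*)^750]². For *r* = 0.05%, 0.1% and 0.2%, the first is 0.687, 0.472 and 0.223, and the second is 0.90, 0.72 and 0.40. The maximum-likelihood OR is then zero, infinite or undefined.

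**The case against.** Several stronger readings are tempting, and the SAP does not support them.

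- **That this is the only safety comparison between arms.** It is not. The descriptive sentence treats AEs, SAEs and SUSARs as three categories, so the natural reading is three comparisons, with SAEs receiving their own OR. Under assumed rates at 750 per arm and two-sided 0.05, that comparison has power of about 0.79 for 3% vs 1%, 0.62 for 4% vs 2% and 0.36 for 2% vs 1%. Sections 9.1.1 to 9.1.3 model all-cause hospital admission, ICU admission and death, and section 9.3 models self-reported fever and respiratory symptoms. A reader therefore cannot infer that the plan is unable to show other harm from BCG.
- **That injection reactions will drive the OR.** The SAP neither names the solicited events nor gives rates. With low or similar solicited rates, the pooled OR barely moves.
- **That a SUSAR comparison is circular, because suspicion of the product is part of the definition.** In a placebo-controlled trial suspicion can arise in either arm, and section 10 restricts who sees unblinded interim results. The label alone does not invalidate a comparison.
- **That a SUSAR OR can never be computed.** Section 4.4 plans Bayesian inference, and a proper prior gives a posterior even with empty cells. With so few events, however, that posterior would largely be the prior.

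It is also fair to say that these endpoints are exploratory, that no decision rule rests on the any-AE OR, that it is not among the listed interim outputs, and that unsolicited events will be tabulated by arm.

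All of this stands and limits the point. It does not supply an effect estimate for non-serious unsolicited AEs, and it does not settle what the slashes mean. If they meant a composite, SAEs would be absorbed as well.

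**Conclusion.** The point holds in a limited form, and its severity is minor. Section 9.1 pools solicited and unsolicited events in the any-AE comparison, although it already separates them for description. The pooled OR is a valid summary of any AE. If solicited reactions are common and unequal, it is not a usable guide to unsolicited events.

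Under the assumed rates, with no unsolicited effect, the pooled OR runs from 1.00 (solicited 2% vs 2%) to 3.86 (50% vs 10%). At 20% vs 5% and independence, an unsolicited OR of 0.71 appears as 1.49. These figures rest on assumed rates, on 750 per arm and, for the reversal, on limited overlap between the two kinds of event. The gap is confined mainly to non-serious unsolicited AEs, on the reading that SAEs are a separate outcome. The SUSAR OR would probably be inestimable or driven by the prior.

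**What to change.** Reword the comparison sentence in section 9.1 to say that:

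1. AE and SAE are separate outcomes, not a composite;
2. an OR with 95% CI is reported for at least one unsolicited AE, and another for at least one solicited event;
3. the separate SAE comparison is kept;
4. SUSARs are listed by arm as counts, without a logistic OR.

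Section 10 refers back to section 9.1, so the SUSAR change carries over to the interim reports.

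The cost is a few lines of SAP text and one or two extra exploratory models. No new data are needed, because the plan already splits the events this way. The extra intervals should be labelled exploratory, like the rest of section 9.

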### 9.2 Absenteeism endpoints

The same modelling approach will be used as for the primary endpoint.

- 9.2.1 number of days of absenteeism, because of imposed quarantine as a result of exposure to SARS-CoV-2 infection
- 9.2.2 number of days of absenteeism, because of imposed quarantine as a result of having acute respiratory symptoms, fever or documented SARS-CoV-2 infection
- 9.2.3 number of days of unplanned absenteeism because of self-reported acute respiratory symptoms

### 9.3 Days with symptoms endpoints

For the following endpoints, the same modelling approach will be used as for the primary endpoint.

- 9.3.1 number of days of self-reported fever ( $\geq 38$  °C)
- 9.3.2 number of days of self-reported acute respiratory symptoms

For the following endpoints, the same modelling approach will be used as for endpoint 8.2 Cumulative incidence of COVID-19 disease

- 9.3.3 the cumulative incidence of self-reported fever ( $\geq 38$  °C)
- 9.3.4 the cumulative incidence of self-reported acute respiratory symptoms

### 9.4 Immunological endpoints

Analysis of immunological endpoints are not pre-specified and will be described in the publication reporting on these endpoints. This related to the following:

- 9.4.1 the incidence and magnitude of plasma/serum antibodies (IgA,M,G) and SARS-CoV-2-specific antibodies at the end of the study period**
- 9.4.2 the incidence and magnitude of total and/or SARS-COV-2-specific mucosal antibodies at the end of the study period**

---

## 10 Interim analyses

---

Interim analyses will be performed starting from 4 weeks after the first enrolled patient and subsequently every 2 weeks. The interim analysis will be performed by the trial statistician unblinded and will not be disclosed to other study team members. Monthly, the results will be provided to the DSMB unblinded. In case of suggested futility or efficacy, the DSMB statistician will independently replicate the full data analysis before drawing conclusions.

The disposition of participants and conduct of the study will be analysed and reported (section 5).

Of the baseline characteristics (section 6), the following will be reported during the interim analysis:

- Hospital of employment
- Age
- Gender
- History of BCG vaccination
- Department of employment
- Whether planned to work on COVID-19 dedicated department
- Position at department of employment
- Average number of working days in the hospital
- Total days of work loss due to illness between 1 January and 15 March 2020

The following endpoints will be analysed and reported in the same way as described in the above sections:

- Primary endpoint, work absenteeism for any reason (section 7). If during any of the interim analyses, the posterior probability of superiority is  $> 0.995$  or the posterior probability of futility is  $> 0.99$ , a conclusion is reached. In case of superiority, the trial will be stopped. In case of futility, the DSMB will take the totality of the data into account in their recommendation to continue or stop the trial.
- Hospital admission due to COVID-19 (section 8.13)
- SAEs and SUSARs (section 9.1)

Please also refer to the DSMB charter for roles and responsibilities and organizational aspects.

---

